- b. Criteria for discontinuing or modifying allocated interventions: The interventions will be stopped, and immediate care provided if any significant adverse effects, such as rapid heart rate, dizziness, nausea, or a significant change in blood pressure, are detected or self-reported by the study participant. Participants with diabetes, cirrhosis, a history of autonomic dysreflexia, caffeine allergies or sensitivities, or females who are pregnant will be excluded from this portion of the study. Due to the diuretic effects of caffeine, subjects will be asked to empty their bladders prior to consumption. Throughout the 30 min wait time and experimentation, blood pressure and heart rate will be monitored. Any adverse effects will be reported and assessed. Our study team will be prepared to discontinue treatment and offer immediate care if any significant adverse effects, such as rapid heart rate, systemic hypertensive event, dizziness, or nausea are detected or self-reported by the subject. We will define a systemic hypertensive event as a systolic pressure exceeding 140 mmHg and/or diastolic pressure exceeding 90 mmHg.^{46,47}
- c. Strategies to improve adherence to intervention protocols: To improve adherence to intervention protocols, participants will complete these protocols within the INSPIRE Laboratory. We will provide participants with a stipend and reimburse them for travel and lodging costs.
- d. Relevant concomitant care and interventions permitted or prohibited during the trial: Patient Monitoring Equipment. Patient Monitor Systems will be used to monitor hemodynamic changes during and following intermittent hypoxia [Smith Medical Systems, USA; Nonin, USA; Welsh-Allyn, USA; Biopac Systems Inc, USA and Masimo; Irvine, CA, USA]. These devices provide estimates of blood pressure, heart rate, oxygen saturation, and pulse rate variability. These measures will be monitored continuously during breathing protocols to ensure subject safety. The blood pressure cuff transducer will be secured around the upper arm during pressure measurements.

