We will quantify overground walking ability using the 10MWT.⁴⁹ Subjects will perform 2 trials each of the 10MWT at their fastest but safe speed with a minimum of 1-minute rest between trials. Average speed across the two 10MWT trials will be used for analyses. The validated assessment tool will provide an indication of return of our subject population to pre-morbid activities following the initial neurological insult. The 10MWT has high inter-rater reliability, and the rating procedure can be accomplished in approximately 30 minutes.

The screening and physical assessment procedures will last approximately 1.5 hours.

To ensure safety, we also will assess pain, spasticity, systemic hypertension, and autonomic dysreflexia prior to and following caffeine and AIH interventions. We routinely measure pain, spasticity, and incidence of hypertension and autonomic dysreflexia as part of our study protocols in persons with chronic SCI.^{32, 33} We will make measurements at baseline, after session 5, and one-week follow-up, and again at two-weeks follow-ups.

Quantify pain: We will assess pain severity using the Wong-Baker FACES scale of 0 (no pain) to 5 (extreme pain).^{59, 60}

DETAILED STUDY PROTOCOL

Quantify spasticity: We will assess spasticity using the Spinal Cord Assessment Tool for Spastic Reflexes (SCATS).⁵⁸ We will quantify total lower extremity spasticity score using the cumulative sum of 3 SCATS subscales: clonus (0=no spasticity; 3=severe), flexor (0=no spasticity; 3=severe), and extensor (0=no spasticity; 3=severe).

Quantify systemic hypertension incidence rate: In addition to monitoring during the intervention, we will measure systolic and diastolic BP at baseline, after sessions 5, and again at follow-ups. We will define a systemic hypertensive event as a systolic pressure exceeding 140 mmHg and/or diastolic pressure exceeding 90 mmHg.^{46, 47}

We will compute hypertension incident rate for each intervention group as the number of hypertensive events divided by the total person-time. We define person-time in units of person-measures (the sum of the total number of BP measurements) taken for each person. Person-measures accounts for the total number of chances for detecting a hypertensive event and accounts for measurements not made due to drop-out or a disqualifying adverse event.⁶³ Finally, we will compute Relative Risk for each Aim as the incidence rate in the dAIH groups over the incidence rate in the dSHAM groups.⁶⁴

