We do not plan to conduct an interim analysis. However, we will impose criteria for discontinuing or modifying allocated interventions. The interventions will be stopped, and immediate care provided if any significant adverse effects, such as rapid heart rate, dizziness, nausea, or a significant change in blood pressure, are detected or self-reported by the study participant. Participants with diabetes, cirrhosis, a history of autonomic dysreflexia, caffeine allergies or sensitivities, or females who are pregnant will be excluded from this portion of the study. Due to the diuretic effects of caffeine, subjects will be asked to empty their bladders prior to consumption. During and between interventions, blood pressure and heart rate will be monitored. Any adverse effects will be reported and assessed. Our study team will be prepared to discontinue treatment and offer immediate care if any significant adverse effects, such as rapid heart rate, systemic hypertensive event, dizziness, or nausea are detected or self-reported by the subject. We will define a systemic hypertensive event as a systolic pressure exceeding 140 mmHg and/or diastolic pressure exceeding 90 mmHg.^{24, 25} We will stop this trial if serious adverse events are directly attributed to the interventions under study.

14. Timing of analysis

All outcomes will be analyzed collectively. We will maintain concealment of the intervention allocation until the completion of data collection.

15. Timing of outcome assessments

Timing of outcome assessments will occur during specified visits. The timepoints of these assessments along with the timepoints for enrollment and interventions are detailed in the timing schedule (Table 1).

Table 1. Timing Schedule for enrollment, interventions, and assessments

Timepoints (days)	Enrollment		Baseline		Intervention			Follow-ups/Washout	
	-5	0	1	2	3	4	5	8	14
Screening and Allocation Timing									
Eligibility screen	x								
Informed consent	x								
Medical clearance	x								
Allocation		x							
Drug script		x							
Intervention Timing									
Placebo+AIH			x	x	x	x	x		
Caffeine+AIH			x	x	x	x	x		
Caffeine+SHAM			x	x	x	x	x		
Assessment Timing									
Primary outcome									
• Walking speed (10MWT, s)		x				x	x	x	
Other outcomes									
• Voluntary leg strength	x				x	x	x	x	
• Spasticity	x				x	x	x	x	
• Spasm frequency	x				x	x	x	x	
• Walking function	x				x	x	x	x	
• Walking distance (6MWT, m)	x				x	x	x	x	
• Walking Balance (TUG, s)	x				x	x	x	x	

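### Dividing hypertensive events by BP readings taken corrects only for loss unrelated to risk, yet the counted event is itself a listed reason to discontinue, so the rate can be understated

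*Combined protocol and SAP*

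**What the plan says.** Protocol 18 (systemic hypertension incidence rate) computes, for each intervention group, the "number of hypertensive events divided by the total person-time". Person-time is counted in "person-measures (the sum of the total number of BP measurements) taken for each person". An event is a "systolic pressure exceeding 140 mmHg and/or diastolic pressure exceeding 90 mmHg". The same paragraph says this denominator "accounts for measurements not made due to drop-out or a disqualifying adverse event", and then forms a relative risk of the dAIH rate over the dSHAM rate.

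Protocol 11b uses the same 140/90 definition. It says "Our study team will be prepared to discontinue treatment and offer immediate care if any significant adverse effects" occur, and its examples of those effects include a hypertensive event. SAP 13 repeats this. Both sections also say, more directly, that interventions will be stopped for significant adverse effects, with a significant change in blood pressure as one example. Neither gives a threshold for that change.

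The documents do not say that every hypertensive event stops treatment, that it ends participation, or that BP readings then cease. By contrast, Protocol 18 says explicitly that an autonomic dysreflexia event ends participation. Nor do they say whether repeat hypertensive events in one person are counted.

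**The concern.** Counting readings as exposure handles loss that has nothing to do with the outcome: someone who moves away contributes fewer readings, and the rate is still right on average. It does not handle loss caused by the outcome. If a first event ends a person's readings, people at high risk contribute few readings and people at low risk contribute all of theirs. The pooled rate then leans towards the low-risk people, and later events in the high-risk people are never seen.

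This is a safety result for caffeine combined with hypoxia. Protocol 18 describes learning whether the combination leads to hypertension, among other harms, as essential. An understated rate errs towards reassurance, and the text tells the reader that the problem has been dealt with.

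**Working it through.** The plan states no hypertension rate, ratio or target, so there is no figure to reproduce. The check asks how far the rate moves if events end readings.

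**Inputs from the documents**
- Readings per round, monitoring included. Protocol 11 records BP every 5th breathing interval; with 15 episodes that is 15/5 = 3. It adds the start and end of walking practice and the end of the session, another 3. Five sessions give 5 × 6 = 30; baseline and two follow-ups make K = 33.
- Readings per round, scheduled only (Protocol 18): baseline, after session 5 and two follow-ups, so K = 4.
- Participants: 20.

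**Assumptions (the documents give none of these)**
- Typical per-reading risk p0 of 1% or 3%.
- Person-level risk p_i with logit(p_i) normal around logit(p0), SD 0, 1.0 or 1.5.
- Share s of events that end the person's readings for that round.

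**Formula.** Expected readings for person i are E[T_i] = (1 − (1 − s·p_i)^K)/(s·p_i). The reported rate is about Σ p_i·E[T_i] / Σ E[T_i]; the full-follow-up rate is the mean of p_i. This is the large-sample value. A simulation with 20 people gives ratios slightly nearer to 1.

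| K | p0 | SD | s | Full rate | Reported/full, formula | Reported/full, 20 people |
|---|---|---|---|---|---|---|
| 33 | 3% | 1.0 | 1.00 | 0.0455 | 0.0307/0.0455 = 0.68 | 0.70 |
| 33 | 3% | 1.0 | 0.50 | 0.0455 | 0.77 | 0.79 |
| 33 | 3% | 1.0 | 0.25 | 0.0455 | 0.85 | 0.86 |
| 33 | 3% | 1.0 | 0.10 | 0.0455 | 0.93 | 0.93 |
| 33 | 3% | 1.5 | 1.00 | 0.0672 | 0.46 | 0.48 |
| 33 | 3% | 0 | 1.00 | 0.0300 | 1.00 | 1.03 |
| 4 | 3% | 1.0 | 1.00 | 0.0455 | 0.93 | 0.95 |
| 4 | 1% | 1.0 | 1.00 | 0.0160 | 0.97 | 0.99 |
| 4 | 3% | 1.5 | 1.00 | 0.0672 | 0.82 | 0.84 |

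In the first row the simulated shift is 0.0454 − 0.0319 = 0.0135, about one standard error (0.0133) of the full-follow-up rate. Keeping the two follow-up readings after a stop moves that row only to about 0.73 to 0.74, because 30 of the 33 readings fall on treatment days. With K = 4, SD 1.0 and follow-ups kept, the ratio is 0.99 to 1.00. If no readings are lost after an event, it is 1.00 whatever the spread of risk.

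**Mechanism.** A smaller denominator alone raises the rate: one event among 20 people with four readings each is 1/80 = 0.0125, and 1/78 = 0.0128 if that person stops after reading 2. The understatement comes from unseen later events and the reduced weight of high-risk people.

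**dAIH/dSHAM ratio.** With an odds ratio of 2, 3% typical SHAM risk, SD 1.0, 33 readings and every event stopping readings, the ratio goes from 1.83 to about 1.67 (1.68 by the formula).

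**Participant-level summary.** The proportion with at least one event in a round needs only the first event, so stopping within the round leaves it unchanged: 0.619 either way in the first row's setting. It is not immune to loss between rounds. If an event also ended the study, the starters of rounds 1 to 3 would be 1, 0.381 and 0.214 of the cohort and those with an event 0.619, 0.166 and 0.076. The pooled proportion would be 0.861/1.595 = 0.54 (about 0.55 with 20 people) instead of 0.62.

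**The case against.** The strongest reply is that nothing shows the bias will occur. The team is prepared to discontinue treatment; that is not an automatic stop, and stopping treatment is not the same as stopping BP readings. Stopping at every event would, in the 33-reading, 3%, SD 1.0 setting, discontinue about 62% of participants in each round. That fits poorly with the plan's 17% attrition and with SAP 20, which expects everyone to complete all three interventions. With 10% of events stopping readings, about 13% are discontinued per round and the ratio is 0.93. The cohort also excludes people with hypertension and cardiovascular disease, which narrows the spread of risk. No test or decision rule hangs on this rate, and individual adverse events and reasons for lost data are recorded anyway.

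Most of this stands, and it limits the size. A reader might infer that the incidence is necessarily biased low, or that it is low because high-risk people leave the denominator. The documents support neither: stopping is conditional, equal risk gives no downward bias, and losing denominator alone pushes the rate up.

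The reply does not rescue the sentence in Protocol 18, which claims the correction for a disqualifying adverse event in particular. Equal risk is also hard to assume when eligibility runs from C2 to L5 and from 18 to 75 years, and prescribed medication continues.

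**Conclusion.** The claim made for the denominator is too strong. It adjusts for the number of readings taken and corrects only for loss unrelated to hypertension risk, while the counted event is itself listed as a reason to discontinue. Understatement is possible, not established. It requires both that events end readings and that risk differs between people.

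Under the assumed inputs the reported rate runs from about 0.70 of the full-follow-up rate (33 readings, every event stops readings) to 0.93 (10% of events do) and 0.95 to 1.00 (four readings per round), all at SD 1.0. Wider differences between people give more bias, for example 0.48 at 33 readings and SD 1.5. The dAIH/dSHAM ratio usually moves less than the rates. A second model, with Beta-distributed risk, 33 readings and a full study stop, took a true ratio of 1.5 to 1.28 at within-person correlation 0.1 and to 1.22 at 0.3. The absolute rates are therefore the main concern. The change is worth making because it is cheap and the result concerns safety.

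**What to change.** In Protocol 18, replace the clause "accounts for measurements not made due to drop-out or a disqualifying adverse event" with a statement that the denominator adjusts only for the number of readings taken and does not correct for readings lost because of a hypertensive event. In the same paragraph, state whether BP readings continue after treatment is stopped and whether repeat events in one person count.

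Make the main hypertension summary, for each intervention, the number of participants with at least one hypertensive event out of those who started that round. Count anyone discontinued for hypertension as having the event, and show other early stops separately by reason. Keep events per reading beside it as a descriptive figure.

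State that participants who leave the study after an event do not enter later rounds, and list them by round, because the proportion does not correct for that.

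The cost is a few sentences in Protocol 18 and a matching line in the SAP, with data already collected. The downside is that repeat events in one person no longer add to the main figure.

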Our study coordinator, study physicians, physical therapists, PI ([name]), and research collaborators recruited subjects using a variety of strategies shown effective in the past. First, the team identified potential subjects using Institutional Review Board (IRB) approved resources to inform persons with SCI that are currently admitted to inpatient rehabilitation/outpatient units of Spaulding Rehabilitation Hospital, Boston University Medical Center, Massachusetts General Hospital, Gaylord hospital, Albany Medical Center, and Maine Medical Center. Subjects also will be recruited by word of mouth and flyers at these facilities. Eligible subjects screened at INSPIRE Laboratory, Spaulding Rehabilitation Hospital Cambridge, MA. At the screening visit, subjects informed of this project, their potential involvement, the possible benefits, and risks, and their right to terminate participation at any time without penalty. Qualifying subjects in agreement with the study details asked to sign the informed consent and HIPAA form approved by Partners IRB. All potential subjects entered the study according to the inclusion/exclusion criteria above and following medical clearance. Experiments will be conducted at the Spaulding Rehabilitation Hospitals.

11. Interventions

- a. Intervention Procedures: This placebo-controlled study will examine the combined effects of caffeine (vs. placebo) and AIH (vs. SHAM) on walking performance in persons with chronic, iSCI. Participants will receive three combinatorial interventions in random order: placebo+AIH, caffeine+AIH, caffeine+SHAM. The order of interventions will be block randomized. The initial screening and evaluation procedures are similar for all participants. For each intervention, participants will complete up to 8 visits/intervention (1 baseline/intervention + 5 treatment days/intervention + 2 follow-up days/intervention). Participants will complete a total of 24 visits (8 visits/intervention x 3 interventions) after the initial screen. Participant enrollment and allocation will be completed during the screening visit. Baseline will be recorded up to 3 days prior to the first intervention.

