Caffeine intervention (caffeine or placebo): Before each intervention round, subjects will be asked to avoid caffeine-containing substances for 48 hrs. (half-life ~7 hrs.)^{21,23} prior to arrival to control for baseline plasma levels of caffeine.²⁰ Subjects will then ingest capsules containing either placebo (sucrose) or caffeine (up to 400 mg). USP and FCC grade caffeine and placebo capsules will be sourced to a private independent compounding pharmacy (Johnson Compounding Pharmacy, Waltham MA, USA). The study PI ([name]) will hold a Class VI Drug License and the study physician ([name]) will write the prescription for caffeine or placebo and have the prescription sent to the compounding pharmacy. The compounding pharmacy will then dispense the caffeine or placebo to the subject for use in the study. Administration will also be overseen by a physician member of the study team.

Persons experiencing caffeine-induced adverse side effects (e.g., dizziness) will be excluded. Since caffeine is a diuretic, we will encourage subjects to empty bladders prior to AIH (or SHAM). To monitor caffeine levels and identify subject-to-subject differences in absorption, blood samples will be collected before capsule consumption and post-AIH or SHAM intervention on days 1 and 5.^{17, 24, 25}

DETAILED STUDY PROTOCOL

Safety considerations for caffeine: Caffeine is commonly used on a daily basis, with an average adult consumption of up to ~6 mg of caffeine per kg of body weight and heavy consumers consuming ≥ 9 mg/kg,^{19, 26} including in persons with SCI.²⁷ High doses of > 6 mg/kg caffeine have been tested in humans for athletic performance enhancement without reported adverse effects.^{20, 28, 29} In persons with SCI, 6 mg/kg has been shown enhance athletic performance without reported adverse effects^{20, 27} and no significant or unsafe changes in blood pressure, heart rate, or respiration were seen.²⁷ Thus, up to 6 mg/kg is within a reasonable and safe range, and that caffeine was safe and well-tolerated by persons with SCI.

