Breathing intervention (AIH or SHAM): Breathing interventions will begin 30 min after caffeine or placebo to approximately coincide with peak plasma caffeine concentrations.³⁰ Participants will don a latex-free, full non-rebreather mask with a custom neoprene head strap while they sit comfortably in a semi-reclined chair. Intermittent gas mixtures will be delivered via automatic adjustment of one-way valves attached to a hypoxia generator [HYP123, Hypoxico Inc., USA].³¹ We will deliver preset air mixtures of $\text{FIO}_2=0.09\pm 0.02$ (hypoxia) or $\text{FIO}_2=0.21\pm 0.02$ (normoxia) for 1.5min at 1 min intervals of room air breathing. The generator will fill reservoir bags attached to a non-rebreathing facemask worn by subjects. Oxygen concentration will be continuously monitored [OM-25RME; Maxtec Inc, USA]. We will take precautions to ensure safety during interventions by monitoring 5-lead electrocardiography (ECG) and recording oxyhemoglobin saturation via pulse oximetry (SpO_2) and heart rate (HR) at 2-second intervals. Respiratory rate (RR) and blood pressure (BP) will be recorded every 5th breathing interval [Dash 4000 Patient Monitor, GE]. We also will record SpO_2 , HR, RR, and BP at the start and end of walking practice and again at the end of each treatment session.

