Safety considerations for AIH: The physiological effects of AIH in humans are well studied and the methods proposed here deemed safe. Daily AIH-induced enhancements in breathing capacity, limb strength, and walking function occurred without significant adverse events in humans with chronic SCI.³²⁻³⁴ Although prolonged chronic exposure to more severe and longer duration hypoxia causes serious morbidity,³⁵ considerable data show that repetitive exposure to brief mild AIH elicits meaningful functional benefits without pathology.^{8, 36, 37} With mild AIH, the severity of hypoxemia, number of episodes, and exposure duration are low (15 episodes per day, 5 days) versus the chronic hypoxia experienced in obstructive sleep apnea (80-400 episodes per day for years^{35, 38}). Daily AIH (10 episodes/day, 7 days) showed no evidence for hypertension or weight loss⁹ or hippocampal gliosis or cell death in rats with SCI.⁸ Prior study in persons with SCI found no adverse events associated with mild exposures of single-day and dAIH (5 days), and all subjects tolerated exposures well.^{32, 33} No changes in mean arterial blood pressure or heart rate were found before and after each treatment or between baseline and the end of the exposure week. No maladaptive changes in cognitive or spasticity were found either, as measured by the Mini-Mental State Examination and Spinal Cord Assessment Tool for Spasticity.

We have taken great care and consideration in establishing a safe AIH protocol for persons with SCI. Rodent studies were developed using modest protocols of dAIH (10, 5 min episodes; 7 days^{8, 9}). In humans, we selected even more modest dosing (15, 1.5 min episodes; up to 5 days).^{32, 33} Our mild AIH dose of 1.5-min duration is based on human studies that delivered short doses of hypoxia ($\text{SaO}_2=80-85\%$) without report of adverse events.^{32, 33, 39, 40} We also based our AIH protocol on the pattern-sensitive effects of dAIH on respiratory motor control that were more dependent on the intermittency and repetition than the duration of the

DETAILED STUDY PROTOCOL

episodes.^{5, 7, 41-43} Such pattern-sensitivity is common to many models of neuroplasticity⁴⁴ including serotonin-dependent plasticity.⁴⁵ Daily exposures in rats (7 days) allowed for further amplification of the gains without eliciting maladaptive changes, such as cell death, hypertension, or weight loss.^{8,9}

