Eligible participants will be screened at the designated site facilities (i.e., INSPIRE Laboratory, Spaulding Rehabilitation Hospital at Boston and at Cambridge sites). At the screening visit, subjects will be informed of this project, their potential involvement, the possible benefits and risks, and their right to terminate participation at any time without penalty. Qualifying subjects in agreement with the study details will be asked to sign the informed consent and HIPAA form approved by Spaulding Rehabilitation Hospital's IRB. All potential subjects will enter the study according to the inclusion/exclusion criteria above and following medical clearance. Experiments will be conducted at the Spaulding Hospital in Cambridge.

Prospective subjects will be contacted by telephone, mail or email and briefly informed of the methods, inclusion criteria, and purpose of the study. We also will provide a description of this study on <http://www.ClinicalTrials.gov>, as required by U.S. law. In all cases, recruitment will not be coercive, will not involve undue inducements, and will accurately reflect the study.

We will recruit individuals who reflect the population of persons with SCI in the Northeast region of the United States, which is 19% women, 81% men, 67% Caucasian, 24% African American, 8% Hispanic, 2% Asian, and 1% Native American. We do not yet know of any differences in responsiveness to AIH or caffeine according to the gender or race of persons with SCI.

Children will not be included in this study. The proposed research is aimed at understanding the plasticity-inducing mechanisms of caffeine and repetitive acute intermittent hypoxia exposure in adults with chronic, incomplete spinal cord injury. A separate study would be required to address the confounding effects of childhood growth and development after spinal injury on the proposed intervention study – a topic best suited for future research once the underlying mechanisms of the intervention are better characterized.

16. Assignment of interventions (for controlled trials)

Assignment of interventions for study participants will be done using allocation sequence generation, concealment, and double-blinded implementation.

- Allocation sequence generation – This study will consist of three blocks: caffeine+AIH, caffeine+SHAM, and placebo+AIH. We will generate the blocked randomization for the study participants using a random number list randomizer (Random.org).⁵⁵ Participants will

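### The hypertension Relative Risk (dAIH over dSHAM groups) does not name its arms, and the only SHAM arm contains caffeine: two of its three readings mix AIH with caffeine

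*Combined protocol and SAP*

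**What the plan says.** Under Quantify systemic hypertension incidence rate, Protocol section 18 plans an incidence rate per arm: hypertensive readings (systolic above 140 and/or diastolic above 90 mmHg) divided by the number of BP measurements. It then defines a Relative Risk, one per Aim, as "the incidence rate in the dAIH groups over the incidence rate in the dSHAM groups".

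The arms are set out in three places. Protocol section 11: "Participants will receive three combinatorial interventions in random order: placebo+AIH, caffeine+AIH, caffeine+SHAM". Protocol section 16 and SAP section 10, in the same words: "This study will consist of three blocks: caffeine+AIH, caffeine+SHAM, and placebo+AIH". SAP section 20 agrees, naming placebo+AIH and caffeine+SHAM as the two controls. There is no placebo+SHAM condition.

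The plan does not say which AIH arm, or whether both, forms the numerator. The SAP text supplied defines no hypertension ratio. The autonomic dysreflexia ratio in Protocol section 18 is simply between groups and does not settle the matter.

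**The concern.** SHAM is given only with caffeine, whereas AIH is given once with caffeine and once without. An AIH-over-SHAM ratio therefore compares AIH with SHAM at the same caffeine exposure only if the numerator is caffeine+AIH alone. With any other numerator, part of the contrast is caffeine against no caffeine, running in the opposite direction to the AIH comparison.

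The ratio is meant to inform safety. Protocol section 18 treats finding out whether these regimens lead to hypertension, among other pathology, as a condition for calling the combination safe to deliver. If caffeine raised hypertensive readings, a mixed ratio would understate an AIH hazard. If caffeine lowered them, it would overstate one. Because the arms are not named, the choice could also be made after the rates are known.

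**Working it through.** The plan states no expected event rate or ratio, so there is no figure of its own to reproduce. The check is algebraic, with assumed effects.

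**All counted readings on treatment.** Let r be the placebo+SHAM rate (not observed here; it cancels), c the caffeine rate ratio and h the AIH rate ratio. Assume multiplicative effects, no interaction and equal readings per arm. Then placebo+AIH = rh, caffeine+AIH = rch and caffeine+SHAM = rc. The three readings are:

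- caffeine+AIH / caffeine+SHAM = rch / rc = h
- pooled AIH / caffeine+SHAM = (rh + rch) / (2rc) = h(1 + c) / (2c)
- placebo+AIH / caffeine+SHAM = rh / rc = h / c

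With no AIH effect (h = 1):

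| c | matched | pooled | placebo+AIH numerator |
|---|---|---|---|
| 0.8 | 1.00 | 1.125 | 1.25 |
| 1.0 | 1.00 | 1.00 | 1.00 |
| 1.25 | 1.00 | 0.90 | 0.80 |
| 1.5 | 1.00 | 0.833 | 0.667 |
| 2.0 | 1.00 | 0.75 | 0.50 |

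With h = 1.5 and c = 2 the three readings are 1.50, 1.125 and 0.75. Unequal readings change the size only: with h = 1, c = 1.5 and caffeine+AIH supplying 40% to 60% of the AIH readings, the pooled ratio is 0.80 to 0.87.

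**Interaction.** Suppose caffeine does nothing under SHAM, and the AIH ratio is 1 without caffeine and 1.5 with it. The pooled ratio is (1 + 1.5)/2 = 1.25, an average of two different AIH effects. So caffeine must leave the rate unchanged under both AIH and SHAM for the readings to agree.

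**Off-treatment readings.** The plan does not say which BP readings count. It says "In addition to monitoring during the intervention, we will measure systolic and diastolic BP at baseline, after sessions 5, and again at follow-ups". Let f be the share of counted readings taken on treatment, and assume off-treatment readings have the same rate in every arm. Relative to background:

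- placebo+AIH = 1 + f(h − 1)
- caffeine+AIH = 1 + f(hc − 1)
- caffeine+SHAM = 1 + f(c − 1)

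Three values of f can be built from the documents:

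- Scheduled readings only (baseline, after session 5, two follow-ups): f = 1/4.
- One reading on each BP day in Table 1: f = 5/8.
- In-session readings included. The regimen is "15 episodes per day, 5 days" and "blood pressure (BP) will be recorded every 5th breathing interval", so 15/5 = 3 per session. Add "BP at the start and end of walking practice and again at the end of each treatment session", 3 more, giving 6 per session and 30 over five sessions. With 3 off-treatment readings, f = 30/33.

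| f | pooled, h = 1, c = 0.8 | pooled, h = 1, c = 2 | pooled, h = 1.5, c = 2 | matched, h = 1.5, c = 2 | pooled and matched, h = 1.5, c = 1 |
|---|---|---|---|---|---|
| 1/4 | 1.03 | 0.90 | 1.05 | 1.20 | 1.125 |
| 5/8 | 1.07 | 0.81 | 1.10 | 1.38 | 1.31 |
| 30/33 | 1.11 | 0.76 | 1.12 | 1.48 | 1.45 |

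Example, f = 1/4, h = 1.5, c = 2: the arm rates are 1.125, 1.5 and 1.25. Pooled = (1.125 + 1.5)/2/1.25 = 1.05; matched = 1.5/1.25 = 1.20.

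The last column shows what a null caffeine effect buys: pooled and matched agree, but both fall short of 1.5 because of dilution. The count of 30/33 also leaves out BP monitoring during the 30-minute wait after the capsule (Protocol section 11b), when caffeine but not AIH is acting, so f is only approximate.

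**Precision.** With E events in each arm and independent readings, the variance of the log ratio is 1/(2E) + 1/E = 1.5/E pooled and 1/E + 1/E = 2/E matched. The widths are in the ratio √(2/1.5) = 1.155. If h = 1, c = 2 and f = 1 (events E, 2E, 2E), the variances are 1/(3E) + 1/(2E) = 0.833/E and 1/(2E) + 1/(2E) = 1/E, a ratio of √(1/0.833) = 1.095.

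**The case against.** A reader might infer from the plural dAIH groups that the plan pools the two AIH arms and so specifies a wrong analysis. The text does not establish that. The same sentence has dSHAM in the plural although there is only one SHAM condition, so the plural proves nothing. The preceding text computes rates arm by arm, and the efficacy prediction in Protocol section 20 sets caffeine+AIH against each control. The clean ratio is at least a plausible intention. This stands: what the documents show is unnamed arms and wording that does not fit the design.

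A reader might also infer that the ratio will hide an AIH hazard. That needs a caffeine effect, and the documents give no event rate for one. Protocol section 11 reports that with 6 mg/kg caffeine in SCI "no significant or unsafe changes in blood pressure, heart rate, or respiration were seen". That statement makes a large c less likely. It does not show equal rates of readings above 140/90 mmHg when AIH is added, and the plan does not state a null caffeine effect as an assumption of the ratio. With c below 1 the distortion runs the other way.

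Nor may one say that a null caffeine effect makes the ratio equal the on-treatment AIH effect. It only makes pooled and matched agree. At f = 1/4, dilution (1.5 to 1.20) costs more on the log scale than mixing (1.20 to 1.05): ln(1.5/1.20) = 0.22 against ln(1.20/1.05) = 0.13. Naming the arms does not cure that.

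Finally, the practical stakes are low. No stopping rule or primary analysis uses this ratio, and the planned arm rates let a reader form the matched one. With N = 20 and an assumed 5 to 10 events per arm, a pooled 95% interval would span a factor of exp(1.96√(1.5/5)) = 2.9 down to exp(1.96√(1.5/10)) = 2.1 either way, wider than the illustrated distortions of the pooled ratio at h = 1. This limits the importance but does not remove the mismatch.

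**Conclusion.** The point holds as a mismatch between a stated rule and the design. Of the three available numerators, only caffeine+AIH gives a clean AIH contrast. The other two differ from it unless caffeine leaves the event rate unchanged under both AIH and SHAM.

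The mismatch is certain from the text; its direction and size are not known. The range 1.125 to 0.75 for the pooled ratio rests on an assumed c of 0.8 to 2, no AIH effect, multiplicative effects, equal readings per arm and every counted reading being on treatment. Off-treatment readings narrow it.

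Impact is minor. This is a secondary, descriptive safety ratio, and the arm-level rates needed to form the right contrast are already planned.

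**What to change.** In Protocol section 18, delete the reference to Aims and define the hypertension Relative Risk as the rate in caffeine+AIH over the rate in caffeine+SHAM, described as the AIH effect with caffeine present. Give it the 95% interval that SAP section 18 already plans for comparisons, and enter the same definition in the SAP.

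As additions rather than corrections:

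- Report caffeine+AIH over placebo+AIH, the caffeine effect with AIH present, which has no named hypertension ratio at present.
- State which BP readings count.
- Use intervals that allow for repeated readings within a participant.

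The cost is wording; no new data are needed. The AIH ratio uses two arms instead of three, so its log-scale interval is about 15% wider than a pooled one under equal event counts and independent readings (about 10% in the h = 1, c = 2, f = 1 case). Without a placebo+SHAM condition, each effect remains estimable only in the presence of the other treatment, and the text should say so.
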